### **COVID-19 Phase 1 Re-Opening:**

For in-person visits to NYSPI, individuals are at increased risk for exposure to COVID-19 both in transit to NYSPI as well as during their time at NYSPI. Procedures are in place to minimize this risk. We plan to offer car transportation subject to a maximum of \$50 each way, which minimizes exposure to public transportation for those participants. At NYSPI, personal protective equipment such as masks will be utilized at all times both by staff and participants, and social distancing will be adhered to when possible (exceptions exist for procedures such as blood draws and EKGs). Screen shields between patient and staff will be used during neuropsychological testing to further minimize exposure risk.

## **Methods to Protect Confidentiality**

Describe methods to protect confidentiality

All records of the participating subjects will be kept in a locked room with access provided only to staff members. Patients' names will be linked with code numbers in a password protected file to which only the research assistant has access. Only these code numbers will appear on all pill bottles and paper measures collected during study. All data collected will be kept confidential and used for professional purposes only. Publications using these data will be done in a manner that protects the subjects' anonymity. All electronically stored data will be accessible by password known only to the principal investigator and research assistants for the study.

### **COVID-19 Phase 1 Re-Opening:**

Due to the implementation of virtual visits, additional measures to protect patient confidentiality will be employed. These include using only secure HIPAA-compliant video conferencing recommended by NYSPI for virtual calls (WebEx, etc.) and the use of headphones during virtual calls.

*Will the study be conducted under a certificate of confidentiality?*

Yes, we have already received a Certificate of Confidentiality

## **Direct Benefits to Subjects**

Direct Benefits to Subjects

No direct benefits to subjects are guaranteed, but individuals may benefit from receiving open

antidepressant treatment and from receiving full amplification hearing aids.

## Compensation and/or Reimbursement

Will compensation or reimbursement for expenses be offered to subjects?

Yes

Please describe and indicate total amount and schedule of payment(s).

Include justification for compensation amounts and indicate if there are bonus payments.

Subjects will be provided **\$125 for completion of MRI at baseline and \$125 for completion of the end point MRI**, paid in the form of a gift card, e-gift card, or check. **Participants could earn up to a total of \$250 for completing MRI procedures.**

All subjects will be allowed to keep their hearing aids following the completion of the study.

To help reduce patients' potential exposure to COVID-19 on public transportation, we will be offering patients paid transportation (subject to a maximum of \$50 limit each way per week) for in-person study visits.

## Uploads

Upload the entire grant application(s)

Upload copy(ies) of unbolded Consent Form(s)

Hearing\_Consent\_11.04.20\_CLEAN.pdf

Upload copy(ies) of bolded Consent Form(s)

Hearing\_Consent\_11.04.20\_BOLD.pdf

Upload copy(ies) of recruitment materials/ads to be reviewed

Hearing Recruitment Flyer.pdf

Hearing\_ad\_with\_tabs\_draft\_11.4.20\_(unstamped).pdf

Hearing\_Newspaper\_ad\_draft\_11.04.20\_(unstamped).pdf

Upload a copy of Certificate of Confidentiality

Upload copy(ies) of the HIPAA form

Upload any additional documents that may be related to this study

## Treating Hearing Loss to Improve Mood and Cognition in Older Adults

The purpose of this study is to determine whether treating hearing loss is helpful for depression over and above the known effects of antidepressants. Age-related hearing loss (ARHL) is the third most common health condition affecting older adults after heart disease and arthritis and is the fifth leading cause of years lived with disability worldwide.

In this 12-week research study, participants will be fitted with hearing aids that may be fully tuned to improve hearing (full dose) or may be only partially tuned and not likely to substantially improve hearing (low dose). Participants will receive free hearing aids that will be at full dose at the end of the study. They will also receive treatment for depression with an FDA approved medication called escitalopram (Lexapro) or duloxetine (Cymbalta). Escitalopram is a Selective Serotonin Reuptake Inhibitor (SSRI) medication, and duloxetine is a Selective Serotonin-Norepinephrine Reuptake Inhibitor (SSNRI) that both appear to help with symptoms of depression.

### You may be eligible if you:

- Are 60 years or older
- Have moderate to severe hearing loss
- Have low mood or feelings of isolation

Eligible participants may receive up to \$250 in financial compensation over the course of participation and free hearing aids.

Scan the QR code above for more information or call [contact] for a free screening to determine your eligibility.

You can also email us at [[contact]](mailto:[contact])

# Do you have hearing loss? Are you feeling down or isolated?

Study looking at the relationship between **hearing loss** and **depression**  
seeking participants ages **60+** with:

- **Moderate** to **severe** hearing loss
- Low mood or feelings of isolation

If you qualify, you may receive:

- Comprehensive cognitive testing
- **Free hearing aids**
- Depression treatment
- Travel compensation
- MRI Scans
- Compensation of up to \$250

Scan the QR code above for more information or call [contact] for a free screening to determine your eligibility.

This study is being conducted at NYSPI/ Columbia University Irving Medical Center

### **Statistical Analysis Plan**

#### MRI Data Preprocessing and Analysis

T1 images were processed using previously published automated segmentation processes identifying cortical and subcortical regions using FreeSurfer, followed by visual inspection of segmentation. Regions within the auditory cortex constituted T1 regions-of-interest (ROIs): cortical thickness of anterior transverse temporal gyrus and superior temporal gyrus (lateral, planum polare, and planum temporale). These were selected due to previous evidence that HL is associated with deafferentation-induced atrophy of primary and secondary auditory cortices in older adults.

DTI ROIs included the inferior fronto-occipital fasciculus, inferior longitudinal fasciculus, superior longitudinal fasciculus (SLF), and uncinate fasciculus. These tracts are important for processing of auditory information and also have been shown to underlie constituent executive functions in older adults. DTI data were processed using FMRIB Software Library (FSL) version 6.0.1 (Oxford, UK). After movement and distortion correction using FSL Eddy, extraction of a brain mask using the Brain Extraction Tool, a diffusion tensor model was fitted using FSL DTIFIT for each voxel and used to generate fractional anisotropy (FA) images. TBSS were applied to the FA images by aligning the images to a 1x1x1mm standard space, creating a mean FA image, and projecting all participants' FA images onto the mean FA skeleton which was then used for statistical analyses. The Johns Hopkins University (JHU) white matter tractography atlas was used to quantify mean FA for the selected ROIs. Nonlinear warps and skeleton projection were also applied to radial diffusivity (RD) images for statistical analyses.

## Data Analysis

Participants were randomized to receive hearing aid treatment vs. sham, and analysis of covariance (ANCOVA) was used to analyze the between-group differences (i.e., active-sham effect) on hearing, psychiatric, functional, and cognitive outcomes. For each measure (i.e., HHIE), the outcome modeled was the change from baseline (Week 0) to the end of study (Week 12) with predictors including baseline HHIE, group (active vs. sham), and covariates of age and education. Encompassing all participants (including those randomized to sham), this model provides baseline adjusted estimates of change within group, i.e. the difference from pre- to post-randomization for the active group, the difference from pre- to post-randomization for the Sham group, and the randomization effect between groups (active-sham effect). Differences in the number of hours of hearing aid usage between groups (active vs. sham) by time (Week 2, 6, 12) was analyzed using an analysis of variance (ANOVA) by including the predictors of group, time, and group by time interaction.

Lastly, association analyses were performed between audiometric measures (PTA and SDS) and mean FA and RD of the specified DTI ROIs using partial correlations and adjusting for age and gender as covariates. The same association analyses were performed between audiometric measures and cortical thickness of our T1 ROIs, adjusting for age, gender, and intracranial volume. Given the small sample size, the exploratory analyses did not control for multiple comparisons.

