## Specific Aims and Hypotheses

### Specific Aims and Hypotheses

**Aim 1:** To investigate baseline relationships between ARHL, CCN circuit measures, and neuropsychiatric measures.

**Hypothesis 1:** More severe ARHL (higher thresholds on pure tone audiometry) will be associated with diminished connectivity and activation within the CCN, which themselves will be associated with poorer executive functioning and increased depressive symptoms.

**Aim 2:** To investigate whether augmentation of standard antidepressant medication treatment with hearing assistive devices is useful for the treatment of comorbid ARHL and LLD.

**Hypothesis 2:** AD + full amplification hearing aids will result in greater depressive symptom improvement (change on Hamilton Rating Scale for Depression [HRSD]) and higher response rates (proportion with Clinical Global Impressions—Improvement [CGI] score of 1 or 2 at endpoint), improved executive functioning, and increased pre-post CCN connectivity and activation compared to AD + low amplification hearing aids.

**Exploratory aims:** To explore the influence of hearing aid compliance (as measured by objective device usage logs) and change in social functioning (as measured by the Social Adjustment Scale—Self Report version [SAS-SR]) on pre-post change in depressive symptoms and executive functioning. We will also attempt to identify pre-treatment participant expectations related to hearing aids as well as participant-identified factors that influence hearing aid use and perceived effectiveness.

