## Description of Subject Population

### Sample #1

Specify subject population

Older adults with hearing loss and depression

Number of completers required to accomplish study aims

32

Projected number of subjects who will be enrolled to obtain required number of completers

40

Age range of subject population

$\geq 60$

Gender, Racial and Ethnic Breakdown

On the basis of previous studies conducted in the Clinic for Aging, Anxiety, and Mood Disorders (CAAM) (formerly the Late Life Depression Research Clinic [LLDRC]) at the New York State Psychiatric Institute (NYSPI) and Columbia University, it is anticipated that the sample at this site will be composed of approximately 75% Caucasian, 15% African American, and 10% Hispanic subjects.

On the basis of previous studies conducted in the CAAM, it is anticipated that the sample recruited will be composed of 60% women and 40% men.

Description of subject population

This study will enroll 40 outpatients who (1) are aged  $\geq 60$  years, (2) diagnosed with Diagnostic and Statistical Manual (DSM) 5 MDD or Persistent Depressive Disorder, (3) have duration of depression  $\geq 6$  months, (4) have 24-item Hamilton Rating Scale for Depression (HRSD) score  $\geq 16$ , (5) have moderate to severe unilateral or bilateral hearing loss (combined PTA  $> 50$ dB at 2 and 3 kHz), (6) demonstrate impaired speech discrimination scores (60-100% on 25 word list testing) in one or both ears, (7) no history of hearing aid use within the past 6 months, (8) English speaking, and (9) are willing to and capable of providing informed consent and complying with study procedures. Exclusion criteria are (1) diagnosis of substance abuse or dependence (excluding Tobacco Use Disorder) within the past 12 months, (2) history of psychosis, psychotic disorder, mania, or bipolar disorder, (3) diagnosis of probable Alzheimer's Disease, Vascular Dementia, or Parkinson's Disease, (4) Mini Mental Status Examination (MMSE)  $\leq 24$  (66), (5) current or recent (within the past 4 weeks) treatment with antipsychotics or mood stabilizers, (6) current suicidal ideation (HRSD suicide item  $> 2$ ) with risk of imminent self-harm, (7) any physical or intellectual disability adversely affecting ability to complete assessments, (8) acute, severe, or unstable medical or neurological illness, (9) contraindication to hearing aid placement, and (10) significant retrocochlear pathology or

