### Overview

Following baseline evaluation and MRI scanning, each subject will be counseled on the role of antidepressant medications in clinically significant depressive disorders as well as the risks and benefits of starting/changing antidepressant medication. Subjects will be randomized to receive antidepressant medication (AD) in combination with either full amplification hearing aids or low amplification hearing aids. Subjects who do not wish to change their antidepressant medication will also be offered participation in a subgroup of the study and will be randomized to receive either full amplification hearing aids or low amplification hearing aids. Subjects, treating clinicians, and depressive/cognitive outcome assessors will be blinded to hearing aid assignment. At randomization (Week 0) subjects will have devices placed and receive education by an audiologist, who will not be blinded but will conduct identical procedures for full vs. low amplification hearing aids and will maintain the blinding with participants. Subjects will have follow up audiology appointments at Weeks 2, 6, and 12 to receive further education, monitor compliance, and ensure devices are working correctly. Failure to adhere to hearing aid use requirements at Weeks 2 and/or 6 (as determined by the usage data log), or any hearing aid complications will prompt an additional audiology appointment at Week 9. At Weeks 2, 4, 6, 9, and 12 subjects will complete depression follow-up visits. However, a weekly CGI severity score of 6 or 7 will prompt a weekly session to check-in with the subject.

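### The efficacy ANCOVA has no rule for a missing Week 12 score and ignores the interim depression scores, although the protocol withdraws participants who worsen

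*SAP*

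**What the plan says.** The SAP (Data Analysis) states that "analysis of covariance (ANCOVA) was used to analyze the between-group differences" on hearing, psychiatric, functional and cognitive outcomes. For each measure, "the outcome modeled was the change from baseline (Week 0) to the end of study (Week 12", with baseline value, group, age and education as predictors. It adds: "Encompassing all participants (including those randomized to sham), this model provides baseline adjusted estimates of change within group". The only model over several time points is an ANOVA of hearing-aid hours at Weeks 2, 6 and 12, which concerns compliance. The SAP contains no imputation rule, analysis-set definition, mixed model or sensitivity analysis.

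The protocol schedules more data than this model uses. The Overview says: "At Weeks 2, 4, 6, 9, and 12 subjects will complete depression follow-up visits". Study Assessments, item 3, lists HRSD, CGI, IDS-SR and the Social Adjustment Scale at the psychiatric follow-up visits. HRSD change comes first in Hypothesis 2: "AD + full amplification hearing aids will result in greater depressive symptom improvement (change on Hamilton Rating Scale for Depression [HRSD".

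Criteria for Early Discontinuation removes a participant whom the clinician judges to have worsened materially, or whose CGI-Improvement is 6 or 7 at two visits in a row. No Week 12 score is planned for anyone so removed. Sample #1 asks for 32 completers and gives 40 as the "Projected number of subjects who will be enrolled to obtain required number of completers".

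**The concern.** A two-point change score needs both points. Without a missing-data rule, the model as written leaves out anyone who lacks Week 12, including people who left because their depression worsened. The interim scores that recorded the worsening are also discarded.

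Two results are exposed. The SAP reports change within each arm, and removing those who worsened makes both arms look better than they were. It also reports the active-sham effect. If the active device works, fewer active participants worsen, so the sham arm loses more of its worst cases and the difference shrinks. If there is no effect but exits work differently in the two arms, the bias can go either way.

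Other exits (low device use, drug intolerance, missed visits, withdrawn consent) may or may not be related to mood. The protocol treats the first as an open question, since it plans "To explore the influence of hearing aid compliance (as measured by objective device usage logs" on depressive change.

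The point does not extend to outcomes measured only at baseline and Week 12, which have no interim scores to use.

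**Working it through.** **Figures in the documents**

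- Sample #1: 32/40 = 0.80, so 40 - 32 = 8 participants (20%) are implied non-completers. In reverse, 32/(1 - 0.20) = 40. The pair is consistent, but this is circular because no dropout rate is stated.
- Research Related Delay to Treatment: 20 participants get low amplification, so 20 per arm.
- Unused data: 40 participants x 4 interim visits = 160 planned HRSD scores.

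**Why completers mislead**

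If a share p of an arm leaves, the arm mean is (1 - p) x completer mean + p x leavers' mean. The completer error is therefore p x (completer mean - leavers' mean). The between-arm error is the difference between the two arms' errors.

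**Assumed inputs**

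The documents give no SD, correlation, effect size or link between CGI and HRSD points. All of the following is assumed:

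- SD 7, true difference 4 (positive favours active), true sham change -4.
- Visits 0, 2, 4, 6, 9 and 12. Four correlation patterns: constant 0.6; decaying at 0.6 or at 0.8 per 3 weeks; 0.4 + 0.6 x decay.
- Recorded worsening: HRSD 4 or 6 above baseline at two consecutive visits, or 4, 6 or 8 above at one visit.
- Unrecorded worsening: the same rise of 4, 6 or 8, but at the next visit, which is not scored.
- Random exits of 5, 8 or 12% in addition. Scenarios kept if total attrition was 14-22%: 22 recorded, 10 unrecorded.
- 60,000 per arm, simulation error about 0.08. Age and education not simulated.

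**Results, true difference 4 and true sham change -4**

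| Exits | Analysis | Difference | Sham change |
|---|---|---|---|
| Recorded worsening | Completers | 3.5 to 3.9 | -4.4 to -5.2 |
| | Repeated measures, baseline-by-visit, unstructured | 3.9 to 4.05 | -4.0 to -4.1 |
| | Same, without baseline-by-visit | 3.8 to 4.05 | -4.0 to -4.5 |
| | Baseline-by-visit, heterogeneous Toeplitz | 3.9 to 4.05 | -4.0 to -4.1 |
| | Baseline-by-visit, AR(1) | 3.8 to 4.0 | -4.1 to -4.5 |
| | Baseline-by-visit, compound symmetry | 3.8 to 4.05 | -3.9 to -4.4 |
| Unrecorded worsening | Completers | 3.2 to 3.7 | -4.7 to -5.6 |
| | Repeated measures | 3.5 to 3.8 | -4.5 to -5.1 |

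With 20% random exits only, completers give a difference of 3.97-4.09, so the bias comes from the worsening exits.

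**Results, true difference 0**

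- Same exit mechanism in both arms: bias within 0.1.
- Recorded-worsening exits in sham only, 20% random exits in active: completers -0.52 to -1.07. Arms reversed: +0.51 to +1.05, a false benefit. Repeated measures: -0.09 to +0.05.
- The same with unscored worsening: errors of 0.7-1.5 (completers) and 0.5-1.0 (repeated measures).

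**Size against the noise**

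At 20 per arm (3,000 trials in each of 8 scenarios) the completer standard error is 2.0-2.5. Bias with a true effect is 0.06-0.35 standard errors. With unequal recorded mechanisms it is about 0.2-0.5. The variance ratio, completer over repeated measures, is 0.90-1.01, so there is no meaningful gain in precision.

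**Dependence on the assumptions**

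- A second set-up let the SD rise from 5 to 7 and removed participants after an observed rise of more than 2 or more than 4 points. Completers gave 3.42 (20% sham and 10% active exits) and 3.64 (8% and 3%) against a true 4.0. Using the interim scores gave 4.00 and 3.98.
- With a stricter trigger (+8 or +10 at two consecutive visits; worsening exits 1-8% in sham), completers gave 3.82-3.97 and sham -4.05 to -4.37.

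**Checks on the remedy**

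- Unstructured covariance over five visits has 5 x 6/2 = 15 parameters. Fixed effects number 17: intercept 1, group 1, visit 4, group-by-visit 4, baseline 1, baseline-by-visit 4, age 1, education 1. The total is 32 for about 40 people. At 20 per arm the fit converged in 193 of 193 trials without age and education, and in 116 of 116 with them.
- In five unrecorded-worsening scenarios, the penalty that restores a difference of 4.0 is 3.7-6.2 points, and the one that restores sham -4.0 is 3.4-6.3. Example: worsening exits of 19.0% in sham and 9.6% in active, penalty 6: 6 x (0.190 - 0.096) = 0.56, moving 3.54 to about 4.1.

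**The case against.** The strongest reply is that the effect on the main comparison is minor. A bias of at most 0.35 standard errors will seldom change a conclusion at 20 per arm, the alternative is no more precise, and with complete Week 12 data the two analyses largely coincide. This stands, and it is why the point is rated a cheap improvement. It does not cover the within-arm changes, where the distortion is larger.

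Second, the sizes rest on invented triggers, since no document converts CGI-Improvement or clinician judgement into HRSD points. The ranges are therefore illustrations, not bounds: the two alternative set-ups fall on either side of them. The direction is the same throughout.

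Third, the false-benefit case needs worsening to drive exit in one arm only. The Overview blinds participants, treating clinicians and outcome assessors, and the discontinuation criteria are common to both arms. That case deserves little weight.

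Fourth, dropping participants is an inference from silence, and the reference list includes work on mixed models and informative dropout. The grant application, which was not supplied, may hold a plan. However, no supplied text applies those references. The sentence on covering all participants may mean only that both arms enter one model, and on either reading it gives no rule.

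Fifth, 32 parameters is a lot for 40 people. Convergence was satisfactory in simulation, but Kenward-Roger inference was not checked and real data may need a simpler covariance.

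Finally, SAS-SR measures social functioning and CGI-S global severity, so neither is strictly a depression scale. Their visit schedule is the same, so the point about unused scores still applies.

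**Conclusion.** The concern holds as a cheap improvement. That the SAP is silent on missing Week 12 data, leaves the interim scores unused and sits beside worsening-based withdrawal can be read directly from the documents, and confidence in this is high.

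The numerical size is conditional on the assumed SD, correlations, triggers and attrition. On those assumptions, completers overstate sham improvement by about 0.4-1.2 points when worsening was recorded and 0.7-1.6 when it was not. They understate a true 4-point difference by about 0.1-0.5 and 0.3-0.8 respectively. Repeated measures removes most of the bias in the first case and only part in the second. With no true effect and the same exit mechanism in both arms, the between-arm bias is about zero.

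**What to change.** 1. For HRSD, IDS-SR and SAS-SR, fit a likelihood-based repeated-measures model in all randomised participants with a baseline and at least one later score. Terms: group, visit (2, 4, 6, 9, 12), group-by-visit, baseline, baseline-by-visit, age and education, with Kenward-Roger degrees of freedom. Use unstructured covariance, falling back to heterogeneous Toeplitz, then AR(1), then compound symmetry as a last resort; state that the last two recover less of the bias. Report the Week 12 contrast and the within-arm Week 12 changes beside the ANCOVA. Treat CGI-S as supportive, or use an ordinal model.
2. Make this the main analysis only if it is specified before unblinded analysis. If the analysis is already done, as the SAP's past tense suggests, keep the ANCOVA as main and label the new model a sensitivity analysis.
3. Add a missing-not-at-random analysis for HRSD. Multiply impute Week 12 by sequential regression on arm, baseline, interim HRSD, age and education. Add 2, 4, 6 and 8 points to the imputed values of those withdrawn for worsening, fit the SAP's ANCOVA and pool.
4. Report the number analysed and the reasons for missing Week 12 data by arm. Reword the SAP sentence on covering all participants to say who is analysed.
5. Reconcile the protocol passages that define exits. On low device use, Hearing aid procedures item 3 disqualifies the participant, whereas the Overview, Study Assessments item 2 and Hearing aid procedures item 4 prescribe an extra Week 9 visit; the Overview's condition reads "Failure to adhere to hearing aid use requirements at Weeks 2 and/or 6 (as determined by the usage data log". These may be sequential steps, but the text does not say so. On drug intolerance, Risks item 2 withdraws the participant, whereas Antidepressant medication item 2 moves them to another drug.
6. Keep the ANCOVA for outcomes measured only at baseline and Week 12.

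The cost is SAP wording and a little analysis of data already scheduled, with no new visits or participants.

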3. Hearing aids will be the latest Audeo B-R 90 devices manufactured by Phonak. Low amplification and full amplification hearing aids will be identical in appearance, battery use, and data logging capability. Low amplification hearing aids will be programmed to prescription for a flat 30dB hearing loss, which will result in a small but noticeable volume increase without substantively improving subject's ability to discriminate speech, which we believe is important for the hearing aids' effect on depressive symptoms. Full amplification hearing aids will have their gain determined by audiometric profile as per standard clinical practice. Real ear measures will be performed to verify fitting, education and counseling will be provided regarding the use of the hearing aid, and subjects will be informed that a minimum of 8 hours/day hearing aid usage is required to stay in the study. To assess compliance with hearing aids, we will measure usage rates (hours/day) using data log technology built into the hearing aids (69-70) Subjects will also sign a hearing aid agreement which includes the provision that if the subject does not complete the 12-week study they must return both hearing aids. If the subject does not complete the 12-week study and would like to keep the hearing aids, he/she can buy the hearing aids at market cost (\$5,300). If a subject does not return the hearing aid, he/she will be charged at market cost for the hearing aid (\$5,300) to the CUMC/Audiology Department. Furthermore, if the subject does not wear the hearing aids for at least 8 hours a day this will disqualify him/her from the study and he/she will have to return all devices. However, if during the study period the subject breaks or loses the hearing aids, we will provide them a new device at no cost to the subject. .

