4. Subjects will have follow up audiology appointments at Weeks 2, 6, and 12, during which their questions about hearing aid usage will be answered and the data log will be checked and reset. At Week 6, if the hearing aid devices are functioning well and the patient is meeting the usage requirement, the audiologist will ask if the patient would like to skip the Week 9 audiology visit and return at Week 12. However, if the patient's hearing aid use does not meet the requirement at Weeks 2 and/or 6 (as determined by the data log) or if there are any hearing aid complications, they will be scheduled for an audiology visit at Week 9. At Week 12, endpoint measures will be collected, which comprise the HHIE and repeat of audiological measurements from Week 0.

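### The SAP's hearing-aid usage ANOVA lists no participant error term for three repeated logs; if fitted as listed, its group test runs at about 12–21% instead of an assumed 5%

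*SAP*

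**What the plan says.** The SAP's Data Analysis section describes the outcome of this analysis as "Differences in the number of hours of hearing aid usage between groups (active vs. sham) by time (Week 2, 6, 12"), and says that it "was analyzed using an analysis of variance (ANOVA) by including the predictors of group, time, and group by time interaction". It names no participant term, random effect, covariance structure or error stratum, and does not call the ANOVA a repeated-measures one.

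The protocol shows where the readings come from. Under Hearing aid procedures, item 3: "we will measure usage rates (hours/day) using data log technology built into the hearing aids". Item 4 of the same section: "Subjects will have follow up audiology appointments at Weeks 2, 6, and 12", and the log is checked and reset at those visits. Each participant can therefore supply up to three usage values, one per visit.

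The protocol gives 32 under "Number of completers required to accomplish study aims", from 40 enrolled. Neither document gives a significance level for this test, a within-participant correlation, or a mean or SD of usage.

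**The concern.** Some people wear their devices for long hours and some do not, and much of that difference persists from visit to visit. Three logs from one person are therefore not three independent pieces of evidence about the arm that person was randomised to. An ANOVA with only group, time and group by time puts differences between participants and visit-to-visit variation into one residual. It then tests group against that residual as if every row were a separate subject.

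This has two opposite effects. The group test gets an error term that is too small, so it can show a difference in wear time that is not there. The group-by-time test gets one that is too large, so it can miss a real divergence over time.

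The stake is the reading of compliance. The protocol's background faults earlier studies for rarely measuring use objectively. Whether the two arms wore their devices equally bears on how an active-versus-sham comparison is interpreted. A reader of the SAP cannot tell whether a reported difference in hours was judged against variation between participants.

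**Working it through.** The plan states no error rate or interval for this analysis, so there is no figure of its own to reproduce. The check asks what the listed model does with repeated logs.

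**Inputs from the documents**
- Model terms: group, time, group by time (SAP, Data Analysis).
- Logs per participant: m = 3 (Weeks 2, 6, 12).
- Participants per arm: n = 16, half of the 32 required completers. Equal split is assumed.

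**Assumptions not in the documents**
- Two-sided level 0.05.
- ICC (ρ) of 0.3, 0.5 and 0.7, with equal correlation between any two visits.
- SD of usage σ = 3 h/day (needed only for the half-widths).
- Complete data.

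**Step 1: the error term used.** With 32 participants and 96 rows, the listed model leaves 96 − 6 = 90 error df. These mix 30 df between participants, with expected mean square σ²(1 + 2ρ), and 60 df within participants, with expected mean square σ²(1 − ρ). The pooled expectation is [30σ²(1 + 2ρ) + 60σ²(1 − ρ)]/90 = σ².

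**Step 2: the error term needed.** The true variance of the group difference is (2σ²/nm)(1 + 2ρ). The listed model uses 2σ²/nm, which is too small by the factor 1 + 2ρ: 1.6, 2.0 and 2.4 at the three ICCs.

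**Step 3: actual size of the group test.** Size = 2[1 − Φ(1.96/√(1 + 2ρ))].

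**Step 4: actual size of the group-by-time test.** Its correct error is σ²(1 − ρ), so the listed model's error is too large. Large-sample size = P(χ² on 2 df > 5.991/(1 − ρ)) = exp[−5.991/(2(1 − ρ))].

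| ICC | 1.96/√(1+2ρ) | Group test, formula | Group test, simulated | Group by time, formula | Group by time, simulated |
|---|---|---|---|---|---|
| 0.3 | 1.55 | 12.1% | 12% | 1.4% | 1.7% |
| 0.5 | 1.39 | 16.6% | 17% | 0.25% | 0.4% |
| 0.7 | 1.27 | 20.6% | 21% | <0.01% | 0.03% |

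The simulated columns come from 20,000 trials per setting with 16 per arm and exact F references. Tested against the right error (group on 30 df, group by time on 60 df), both tests stay at about 5%. With 20 per arm, the number enrolled, the group-test figures are essentially the same.

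**Step 5: interval width at ICC 0.5, σ = 3 h, 16 per arm.**
- As listed: t(90) × σ√(2/48) = 1.987 × 3 × 0.2041 = 1.22 h.
- Correct: t(30) × σ√[(2/48)(1 + 2 × 0.5)] = 2.042 × 3 × 0.2887 = 1.77 h.

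The average simulated half-widths are 1.21 h and 1.75 h. They are slightly smaller because an estimated SD averages a little below the true one.

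**The case against.** The strongest reply is that nothing shows an error was made. Group, time and group by time are also how a repeated-measures ANOVA is commonly summarised, and this SAP is a short past-tense account that gives no degrees of freedom or software for any of its group-comparison models. That stands: a reader might infer that the test was run wrongly, and the documents do not support it. They support only that the model as listed omits the participant. The SAP does give an explicit list of predictors, however, and fitting that list would give wrong error bars. This is therefore more than a missing technical detail.

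A second reply is that the consequence is small. That also stands. This is one compliance comparison, and no hypothesis in the protocol's Specific Aims tests usage between arms. The exploratory aim concerns usage in relation to change in outcomes. A reader might carry the concern over to the efficacy results, but the efficacy ANCOVA uses one change score per participant and has no repeated rows.

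A third point is the 8 hours/day requirement. It is tempting to say how far the inflation changes once low users are removed, because truncation lowers the remaining correlation. The documents do not allow it. Such a figure needs a mean and SD of usage and an exclusion rule, and none of these can be taken from the documents. Hearing aid procedures, item 3, says that "if the subject does not wear the hearing aids for at least 8 hours a day this will disqualify him/her from the study". The Overview says: "Failure to adhere to hearing aid use requirements at Weeks 2 and/or 6 (as determined by the usage data log") leads to an extra audiology visit at Week 9, and Study Assessments item 2 and Hearing aid procedures item 4 say the same. These passages must be reconciled. No error rate is claimed under that rule.

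**Conclusion.** The point holds as a minor one. The SAP lists a model for repeated usage logs without a participant effect or repeated-measures error term. If it was fitted as listed, the group test rejects about 12% to 21% of the time under no effect, its interval is about 30% too narrow at ICC 0.5 (1 − 1.21/1.75 = 0.31), and the group-by-time test is too conservative. These sizes rest on complete data and on an assumed level, ICC and equal correlation between visits. The hours also rest on the assumed SD of 3 h and 16 per arm. If participant was in fact the error unit, the analysis is sound and only the description needs correcting.

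**What to change.** State participant as the error unit in the SAP's Data Analysis section. The preferred form is a mixed model with group, visit, group by visit and a participant random intercept, because it keeps participants with a missing log. A repeated-measures ANOVA that tests group against between-participant error would also do. If one of these was already fitted, one sentence closes the point. If not, refit the existing logs and report the group difference in hours with its corrected interval.

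No new data are needed. The cost is a wider interval for the group difference, for example 1.75 h instead of 1.21 h half-width at ICC 0.5 under the assumptions above.

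Separately, reconcile the protocol passages on use below 8 hours/day, and state in the SAP which participants' logs entered this comparison.
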